
of fat grafts in a wide arena of clinical situations. Specifically to this application over 100 references were directly pertinent to fat grafting knowledge required for this proposal. We propose a prospective, randomized clinical study to assess the efficacy of minimally invasive autologous fat transfer addressing pain and poor prosthetic fit at amputation sites. Objective: The objective of this study is to assess the efficacy of minimally invasive autologous fat transfer at the amputation sites and the modulation of pain at the respective sites. We hypothesize that autologous fat grafting can provide a minimally invasive therapy facilitated by enabling technology of specialized instrumentation to effectively mitigate pain syndromes at amputation sites, by introducing volume stable subcutaneous tissue over bony prominences and peripheral nerve trunks, thereby avoiding surgical revisions and preserving limb length. We further hypothesize that enriching the fat graft with autologous adipose stromal cells utilizing the Tissue Gensis Cell Isolation System (CIS), a regenerative medicine approach, will lead to improved retention of the fat graft over time and result in a more favorable outcome. Specific Aims: 1) Treat painful amputation sites in 30 patients with fat grafting to provide additional subcutaneous tissue padding over bony structures and nerve trunks. Limb anatomy and healing of the graft over time, along with stability/persistence of the new tissue, will be assessed by high resolution CT scanning with 3D reconstruction. Patients will be followed for 24 months after treatment to define long term outcomes. The primary outcome measures will be pain at the amputation site and improved ability to tolerate a prosthesis. Patients will be randomized to receive either standard fat grafting (15 patients) or cell enriched fat grafting (15 patients). Patients will be enrolled who have pain at an amputation site that limits function and/or interferes with the ability to use a prosthesis. 2) Assess biologic properties of the cells within the fat graft and correlate with clinical outcomes. This will include adipose stem cell yield per volume of fat tissue, cell proliferation, capacity for adipogenic differentiation, lipolysis, and cell sub-population analysis by multiparameter flow cytometry. Results of these assays will be correlated with graft volume retention to search for predictors of good clinical outcome that are related to variation on adipose biology between subjects. 3) Measure quality of life in patients before and after autologous fat grafting using validated psychosocial measures. This will include, among other tools, SF 36, the Beck inventory, and instruments designed for assessing limb function. Study Design: Single center site, prospective, randomized, pilot outcomes study with treatment performed at the University of Pittsburgh. The primary outcome measurements will be: 1) fat graft retention at the amputation site; and 2) improved ability to tolerate a prosthetic device. This study will examine if fat grafting with cell enrichment using the Tissue Gensis Cell Isolation System, (CIS) will demonstrate increased fat retention and decreased pain compared to standard fat grafting alone. Clinical Impact: This study will significantly impact military trauma care by validating a minimally invasive cell based technique for alleviating pain at amputation sites and improving function with a prosthesis. Importantly, the goal will be reached without invasive surgery, increased risk, and a prolonged recovery. Given the high amputation rate in the current conflicts, this work is highly relevant to the care of the wounded warrior. A major

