5 Health-related biomedical or behavioral outcome is defined as the pre-specified goal(s) or condition(s) that reflect the effect of one or more interventions on human subjects’ biomedical or behavioral status or quality of life. Examples include: positive or negative changes to physiological or biological parameters (e.g., improvement of lung capacity, gene expression); positive or negative changes to psychological or neurodevelopmental parameters (e.g., mood management intervention for smokers; reading comprehension and /or information retention); positive or negative changes to disease processes; positive or negative changes to health-related behaviors; and, positive or negative changes to quality of life.

CS18.0 * Based on the above information, does this study meet the NIH definition of a clinical trial? Yes No

If Yes, click Save and then Click Here For Study Team's CITI Training Records . Please ensure all personnel's training is up to date

[reviewer notes-]

Section 1 - Study Objective, Specific Aims, Background and Significance

1.1 Objective: What is the overall purpose of this research study? (Limit response to 1-2 sentences.)The objective of this study is to assess the efficacy of minimally invasive autologous fat transfer at the amputation sites and the modulation of pain at the respective sites. We hypothesize that autologous fat grafting can provide a minimally invasive therapy facilitated by enabling technology of specialized instrumentation to effectively mitigate pain syndromes at amputation sites, by introducing volume stable

Section: Section 1 - Objective, Aims, Background and Significance

subcutaneous tissue over bony prominences and peripheral nerve trunks, thereby avoiding surgical revisions and preserving limb length. The premise of this study is that we will compare two minimally invasive techniques as an alternative to invasive operations, with the understanding that this therapy does not preclude more invasive procedures in the future. We further hypothesize that enriching the fat graft with autologous adipose stromal cells utilizing the Tissue Genesis Cell Isolation System (CIS), a regenerative medicine approach, will lead to improved retention of the fat graft over time and result in a more favorable outcome.

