- 1.2 Specific Aims: List the goals of the proposed study (e.g., describe the relevant hypotheses or the specific problems or issues that will be addressed by the study).1) Treat painful amputation sites in 30 patients with fat grafting to provide additional subcutaneous tissue padding over bony structures and nerve trunks. Limb anatomy and healing of the graft over time, along with stability/persistence of the new tissue, will be assessed by high resolution CT scanning with 3D reconstruction. Patients will be followed for 24 months after treatment to define long term outcomes. The primary outcome measures will be pain at the amputation site and improved ability to tolerate a prosthesis. Patients will be randomized to receive either standard fat grafting (15 patients) or cell enriched fat grafting (15 patients) utilizing the Tissue Genesis Cell Isolation System (CIS). Patients will be enrolled who have pain at an amputation site that limits function and/or interferes with the ability to use a prosthesis.2) Assess biologic properties of the cells within the fat graft and correlate with clinical outcomes. This will include adipose stem cell yield per volume of fat tissue, cell proliferation, capacity for adipogenic differentiation, lipolysis, and cell sub-population analysis by multiparameter flow cytometry. Results of these assays will be correlated with graft volume retention to search for predictors of good clinical outcome that are related to variation in adipose biology between subjects.3) Measure quality of life in patients before and after autologous fat grafting using validated psychosocial measures. This will include, among other tools, SF 36, the Beck inventory, and instruments designed for assessing limb function.

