in the current FDA-approved product labeling for that device (i.e., for an “off-label” indication)?

* No

- 2.2.2.1.1 List each of the devices being evaluated for an “off-label” indication. Specify for each listed device the corresponding Investigational Device Exemption (IDE) number for this device/research study; or provide a justification for why you feel that this device and its “off-label” use, as proposed in this research study (i.e., to include potential failure of the device) constitute a non-significant risk to the involved research subjects.

*

| Device | IDE # | Non-significant risk justification |
|--------|-------|------------------------------------|
|--------|-------|------------------------------------|

There are no items to display

[reviewer notes-]

Section 2 - Research Design and Methods

- 2.3 Summarize the general classification (e.g., descriptive, experimental) and methodological design (e.g., observational, cross-sectional, longitudinal, randomized, open-label single-blind, double-blind, placebo-controlled, active treatment controlled, parallel arm, cross-over arm) of the proposed research study, as applicable.

Prospective, Randomized, Non-blinded, Surgical outcomes, Pilot study assessing clinical outcomes following fat grafting for pain at amputation sites (with and without adipose stem cell enrichment).

- 2.3.1 Does this research study involve a placebo-controlled arm?

* No

[reviewer notes-]

Section 2 - Research Design and Methods

- 2.4 Will any research subjects be withdrawn from known effective therapy for the purpose of participating in this research study?

Section: Section 2 - Research Design and Methods

* No

- 2.4.1 Provide a justification for discontinuing subjects from known effective therapy for the purpose of study participation.
- 2.4.2 Describe the risks to subjects associated with discontinuing them from known effective therapy for the purpose of study participation.

[reviewer notes-]

Section 2 - Research Design and Methods

- 2.5 Will screening procedures (i.e., procedures to determine research subject eligibility) be performed specifically for the purpose of this research study?

* Yes

- 2.5.1 List the screening procedures that will be performed for the purpose of this research study. Do NOT include the inclusion/exclusion criteria in this section as they will be addressed in section 3; questions 3.13 and 3.14.

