
recordings. 3.) All participants who are women of child bearing potential will receive a urine pregnancy dip test. If the test result is positive the subject will not continue participation in this research study. 4.) Collection and review of new medications to include prescription and vitamins / supplements, allergies and vital signs (Temp, HR, Resp, BP), weight, body mass index (BMI) calculation, and adverse event reporting. 5.) Serial Computed Tomography Imaging or MRI scan will be performed. A high resolution Computed Tomography (CT) Scan of the amputation stump will be performed at Presbyterian Hospital and will take approximately 60 minutes. This scan will be pre-procedural and will serve as a baseline. All CT scans will be performed on a 64-slice scanner (LightSpeed, GE Healthcare), using slice thickness of 1.25 mm and pitch of 1.375. kVp, mA, and FOV will be optimized to the subject and body part to be imaged. Soft tissue and bone kernels will be employed. These images will be volumetrically reformatted into coronal and sagittal planes for confirmation of findings. Additionally, surface-rendered volumetric reformats will be created emphasizing both bony structures and soft tissues. In the event that a CT scan is contraindicated or declined by a study participant, MRI will be performed using a 1.5 T MRI scanner (Signa HDx, GE Healthcare). The MR imaging protocols will include coronal and axial planes using T1-weighted spin echo sequences as well as coronal, axial, and sagittal planes using T2-weighted fast spin echo with fat suppression and/or short tau inversion recovery (STIR) sequences. Again, FOV, TR/TE time, acquisition time and other parameters will be optimized to the subject and body part to be imaged. Intravenous contrast will not be administered for either CT or MR imaging. Images will be reviewed by radiology. Volume measurements of the implanted material will be made on all post-procedural CTs or MRIs. These volumetric measurements are expected to be precise to within 5% of the actual volume of material. Trends in volume of tissue will be analyzed over time across the multiple CT or MRI scans. Both linear and volumetric measurements will be used to quantify implanted material. Subjects must remove compression sleeves prior to CT scans. 6.) To further evaluate pre-surgical amputation stump pain, the study coordinator will provide a Pain Assessment form to the participant to complete. This form will document the nature/charter of the discomfort limiting function and or interferes with their ability to use a prosthetic device. The subject will be instructed to document the discomfort to include frequency, location, intensity (1 to 10 scale with 10 as most intense), type of pain (physiological or phantom). It will include self interventions related to pain and use of prosthetic devices. 7.) Psychosocial Assessment: One of the aims of the proposed study is to evaluate pre- and post-operative quality of life and symptoms of psychological distress. This aim will also consider psychosocial factors (pre- and post- surgery) that predict psychological well-being and quality of life outcomes following surgery. The aim is important for identification of psychosocial factors that may play a role in and be critical to enhancing quality of life outcomes from amputation stump surgery. Participants will be asked to complete a psychosocial battery that includes: a) self-report measures of satisfaction with physical appearance, anxiety and depressive symptoms, social functioning and social avoidance and distress and; b) questionnaires that assess significant predictors of quality of life

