Pain and Serial computed tomography imaging will be performed and measured as parametric data sets before fat grafting and afterwards at various time points using a paired t-test model. Repeated measures analysis of variance will be used to evaluate change over time in all outcome measures. Using standard conventions of alpha=0.05 and beta=0.8, an enrollment of thirty patients may provide sufficient power to detect a Cohen's effect size of about 0.9 which is anticipated to be adequate for detecting clinically meaningful differences in the volume of soft tissue. A composite functional score will be constructed from the prosthetics and occupational therapy evaluations and compared between study groups. The details of this analysis, including which evaluations will be included in the score and relative weight, can be best determined as the study progresses and initial data sets are acquired. Additionally, each assessment score from the specific tests will also be considered individually for comparison.

[reviewer notes-]

Section 2 - Research Design and Methods

2.19

Will this research be conducted in (a) a foreign country and/or (b) at a site (e.g., Navajo Nation) where the cultural background of the subject population differs substantially from that of Pittsburgh and its surrounding communities?* No

Note that copies of training records, licenses, certificates should be maintained in the study regulatory binder and are subject to audit by the Research Conduct and Compliance Office (RCCO).

Section: Section 2 - Research Design and Methods

In addition, individuals planning to conduct human subject research outside the United States must complete an optional module on the CITI training website: International Studies. Click [here](#) to access the instruction sheet for accessing optional CITI modules.

- 2.19.1 Address the following for each of the foreign/culturally different sites where this research will be conducted:
- Name of site
 - Name of authorized individual (e.g., IRB Chair) from the local IRB or other human subject protections entity that is responsible for the review and approval of the project; upload approval letter with an English translation, if applicable
 - Name and qualifications of the site collaborator responsible for the conduct of the research (e.g., site PI)
 - The anticipated number of subjects that will be enrolled at that site
 - If Federally funded, provide the Federalwide Assurance number (FWA) assigned to the site *

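### Graft volume has no specified between-arm analysis and no adjustment for mL injected, and 15 per arm at d = 0.9 gives 66% two-sided power, not 80%

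*Combined protocol and SAP*

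**What the plan says.** **Hypothesis and outcome.** Section 1.1 expects that enrichment "will lead to improved retention of the fat graft over time". Statements of what is primary differ. The Study Design paragraph of the abstract (CS2.1) says "The primary outcome measurements will be: 1) fat graft retention at the amputation site", with prosthesis tolerance second. Aim 1 (section 1.2, repeated in the abstract) says "The primary outcome measures will be pain at the amputation site and improved ability to tolerate a prosthesis", and 3.12 likewise names pain and prosthesis wear. Section 2.17 lists pain, prosthesis tolerance and a stable volume of fat, and says they will be compared between the two groups of 15. Aim 2 uses retention as a per-patient variable: "Results of these assays will be correlated with graft volume retention".

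**Measurement.** Section 2.6, item 5, plans to measure the volume of implanted material on every scan after surgery. It adds "These volumetric measurements are expected to be precise to within 5% of the actual volume of material" and "Trends in volume of tissue will be analyzed over time across the multiple CT or MRI scans". There is one scan before surgery, then scans at post-operative visits 4, 5 and 6 (months 6, 12 and 24; section 2.7). The radiation figures in 5.1 agree: 5.2 rem / 1.3 rem = 4 scans.

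**Amount injected.** The surgeon sets it by clinical judgement with help from CT, up to 300 mL in either arm (2.6, Fat Graft Placement). Section 2.6 expects it to vary between patients. Inclusion criterion 10 (3.13) admits defects of about 5 to 300 cc.

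**Analysis.** Section 2.18 names a paired t-test before and after grafting at unspecified times, and a repeated-measures ANOVA of change over time. It states alpha 0.05 and beta 0.8, with thirty patients giving power for a Cohen's effect size of about 0.9, described as "adequate for detecting clinically meaningful differences in the volume of soft tissue".

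The IDE protocol (CS10.1) and the grant application (Supporting Documentation) are listed as attachments but were not supplied. Statements below that something is absent refer to the supplied text.

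**The concern.** The question that separates the two arms is how much of the injected fat survives. The plan measures what is present from month 6 onward, but no scan shows what was there at the start: the baseline scan precedes grafting. The only direct measure of the starting graft is the mL injected, and no passage divides by it or adjusts for it.

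If injected volume varies as widely as the eligible defects, most of the variation in measured mL is variation in graft size. That swamps a difference in survival when the arms are compared on unadjusted mL. A real benefit of enrichment could be missed, and a null result would be hard to interpret.

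The power sentence adds to this. It attaches an effect size to soft-tissue volume without an SD, a difference in mL or percentage points, or sidedness. It therefore cannot be translated into a retention difference.

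**Working it through.** **1. The plan's own power figure.** Inputs from 2.17 and 2.18: 15 per arm, alpha 0.05, d = 0.9. Beta 0.8 is read as power 0.8; taken literally it would mean 20% power.

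Noncentrality = d × √(n/2) = 0.9 × √7.5 = 2.465, with 28 degrees of freedom.

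- Two-sided t-test: power 0.663 (normal approximation: 2.465 − 1.960 = 0.505, power 0.693).
- One-sided t-test: power 0.776 (normal approximation: 2.465 − 1.645 = 0.820, power 0.794, or 16 per arm for 80%).
- 80% power two-sided at 15 per arm needs d of about 1.06. At d = 0.9 it needs about 20 per arm.
- The paired t-test that 2.18 names would detect d = 0.53 with 30 patients or 0.78 with 15 (two-sided, 80% power), so it is not the source of 0.9.

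The stated figure reproduces approximately as a one-sided comparison between arms, which 2.18 does not state.

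**2. What variation in graft size does to raw mL.** Assumptions, none of them in the documents: retention 50% v 65%, SD 15 points, retention independent of graft size, same distribution of injected volume V in both arms, no scan error. Retained mL is Y = V × f, where f is the retained fraction with mean m and SD s:

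mean(Y) = m × E[V]; var(Y) = E[V²] × (m² + s²) − (m × E[V])².

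For V uniform on 5 to 300 mL: E[V] = 152.5 and E[V²] = 295²/12 + 152.5² = 30,508.

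- Standard arm: mean 76.25; variance 30,508 × 0.2725 − 76.25² = 2,499.
- Enriched arm: mean 99.125; variance 30,508 × 0.445 − 99.125² = 3,750.
- Pooled SD = √((2,499 + 3,750)/2) = 55.9; d = (99.125 − 76.25)/55.9 = 0.41.

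A fraction-scale effect of 15/15 = 1.0 has shrunk to 0.41. The same steps give d of 0.23 (log-uniform 5 to 300), 0.66 (uniform 50 to 150) and 0.79 (uniform 100 to 200).

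**3. Simulated power.** 15 per arm, two-sided 0.05, one visit; 20,000 trials per cell in the first five rows. The covariate model is retained mL on arm and mL injected, without limb stratum.

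| Analysis | Uniform 5–300 | Log-uniform 5–300 | Uniform 50–150 | Uniform 100–200 |
|---|---|---|---|---|
| Raw mL, no error | 18% | 8% | 41% | 56% |
| Covariate model, no error | 62% | 42% | 71% | 73% |
| Raw mL, 5% + 5 mL error | 18% | 9% | 39% | 53% |
| Covariate model, 5% + 5 mL error | 58% | 36% | 65% | 69% |
| Fraction (mL / mL injected), 5% + 5 mL error | 56% | 22% | 68% | 71% |
| Raw mL, two-scan subtraction | 14% | 7% | 15% | 24% |
| Covariate model, two-scan subtraction | 24% | 10% | 16% | 26% |

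The 5% is the plan's stated precision, taken as an SD; the 5 mL is assumed. The last two rows assume that volume is obtained by subtracting two scans of a 500 mL region, each with 5% error.

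**4. Could the named ANOVA rescue raw mL?** Giving it an arm-by-time term over the four scans (assumed within-patient correlation of retention 0.9, no error) yields 19%, 8%, 42% and 57%, essentially the raw-mL row.

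**5. False positives.** With equal retention and equal fill, the raw-mL comparison rejects in 5.1%, 4.5%, 4.9% and 5.0% of trials, and the covariate model in 4.8%, 4.3%, 5.2% and 5.0%.

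**The case against.** Much of the structure is already there. Section 2.6 names the quantity to be measured, 2.7 fixes the scan visits, and 2.17 promises a comparison between groups. What is missing is the choice of analysis visit, the test, and any use of mL injected. It would be wrong to say that the plan has no volume measure, no scan schedule or no intention to compare the arms.

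Absolute volume is also a coherent outcome. Padding is the clinical purpose, and 2.17 and 2.18 both speak of volume. That stands: volume should stay as the padding outcome. It does not answer the retention hypothesis in 1.1 or Aim 2.

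The trial calls itself a pilot, and the retention values, SDs and volume spreads above are assumed; the 50–150 and 100–200 mL cases have no source in the documents. So the power figures are illustrations. But 2.18 does make a power claim about volume, and raw mL loses to the covariate model in every case shown.

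A reader might infer that raw mL produces false claims of benefit. The documents do not support that. CT-guided volume, one 300 mL cap for both arms, and filling any shortfall in the enriched arm with standard graft (2.6) point towards similar fill. A difference in fill is possible in a "Prospective, Randomized, Non-blinded, Surgical outcomes, Pilot study", but it is not shown. Only with an assumed 20% difference would raw mL reject in 6% to 37% of trials at equal retention, and even then the volume difference itself would be real.

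A reader might also infer that dividing by mL injected settles the matter. With 5 mL of error the fraction does worse than the covariate model in both cases that use the 5–300 cc range. If fill differs by 20% and retention also falls 30 points across that range, its type I error rises to 5.5–8.3%, against 4.0–4.7% for the covariate model.

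**Conclusion.** The point holds as a loss of power and an incomplete analysis, not as a bias. The supplied text gives no analysis visit, no named between-arm test of graft volume and no adjustment for mL injected, for an outcome that is the trial's stated hypothesis. Under the assumptions above, adjusting for mL injected raises power from 18%, 8%, 41% and 56% to 62%, 42%, 71% and 73%. The gain is largest where graft sizes vary most. It shrinks with scan error and mostly disappears if volume comes from subtracting two large regional volumes, so the planned direct measurement of implanted material should be kept.

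The power statement needs correction regardless of those assumptions: 15 per arm at d = 0.9 gives 66% two-sided and 78% one-sided.

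This should be fixed. Confidence in the absence of a specification is limited by the attachments not supplied; the size of the power loss rests on assumed inputs.

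**What to change.** 1. In 2.18, define the between-arm retention analysis as a linear model of the implanted-material volume already planned in 2.6, at one named existing scan visit (for example month 24, matching the long-term aim), on arm, limb stratum and mL injected. Keep absolute volume as the padding outcome in 2.17. Report implanted volume / mL injected as supportive only.
2. Because mL injected is set after randomisation in a non-blinded trial, tabulate it by arm. Add a sensitivity analysis adjusting instead for baseline CT defect volume, if that is measured. If fill departs from defect with a CV of 20%, that model has 47%, 30%, 50% and 52% power without scan error, against 18%, 8%, 34% and 43% for raw mL.
3. Require mL injected in the intraoperative source document in both arms; 2.6 expressly requires only the cell dose. State whether the 3–8 cc of SVF suspension is included. For 5 mL retained from 10 mL, 5/10 = 50% becomes 5/13 = 38% to 5/18 = 28%; for 50 mL from 100 mL it becomes 50/103 = 49% to 50/108 = 46%.
4. Restate the power sentence with its scale and sidedness: about 66% two-sided at d = 0.9, or 80% at d of about 1.06. Change beta 0.8 to power 0.8.
5. Reconcile the abstract, 1.2, 2.17 and 3.12 on whether imaging is primary.

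The cost is one recorded number per patient, one extra model with its sensitivity analysis, and a less favourable stated power. No scan, visit or treatment changes.
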